6.12.2 Laboratory Data

Descriptive statistics, including 95% confidence intervals, of the observed values and change from baseline (continuous data) will be presented by treatment group and visit for each hematology, urinalysis and serum chemistry continuous parameter. Each measurement will be classed as below, within, or above normal range, based on ranges supplied by the laboratory used. Shift tables in relation to the normal range from baseline to each follow-up visit will be presented.

Analysis of all samples for hematology, chemistry, hepatic function, lipid profiles, and urinalysis will be performed at a central laboratory using standard validated methods (see the laboratory manual). All study data analyses involving laboratory values will be based on results from the central laboratory.

The table below shows the tests, parameters, and time points that will be summarized by treatment arm. For the screening time points, only the last non-missing measurements will be included in the summary.

QMD Ref: [REDACTED]	Effective: 12Aug2019	Governing QMD: [REDACTED]
Confidentiality Statement		
This document is the property of [REDACTED] and may not be duplicated, copied, altered or removed from company without prior approval from [REDACTED] or in compliance with [REDACTED].		
REF: [REDACTED]		Page 31 of 37

		Controlled Quality Management Document	
		Sponsor:	Aurinia Pharmaceuticals
		Protocol Number:	AUR-VCS-2016-02
STATISTICAL ANALYSIS PLAN. PHASE 2-3-4			

Table 2.5 Laboratory Parameters

Test Type	Test Parameters	Collection at Visits
Hematology	Complete blood count (CBC)	All visits
	Hematocrit	
	Hemoglobin	
	Mean corpuscular hemoglobin (MCH)	
	Mean corpuscular hemoglobin concentration (MCHC)	
	Mean corpuscular volume (MCV)	
	Platelet count	
	Red blood cells (RBC)	
	Red blood cell morphology	
	White blood cells (WBC)	
	Differential (absolute and %)	
	Bands	
	Basophils	
	Eosinophils	
Lymphocytes		
Monocytes		
Neutrophils		

QMD Ref: [REDACTED]	Effective: 12Aug2019	Governing QMD: [REDACTED]
Confidentiality Statement		
This document is the property of [REDACTED] and may not be duplicated, copied, altered or removed from company without prior approval from [REDACTED] or in compliance with [REDACTED].		

REF: [REDACTED]

		Controlled Quality Management Document	
		Sponsor:	Aurinia Pharmaceuticals
		Protocol Number:	AUR-VCS-2016-02
STATISTICAL ANALYSIS PLAN. PHASE 2-3-4			

Test Type	Test Parameters	Collection at Visits
Blood Chemistry	Alanine aminotransferase (ALT)	All visits
	Albumin	All visits
	Alkaline phosphatase (ALP)	All visits
	Aspartate aminotransferase (AST)	All visits
	Bicarbonate	All visits
	Bilirubin (direct and total)	All visits
	Blood urea nitrogen (BUN)	All visits
	Calcium	All visits
	Chloride	All visits
	Cholesterol (total, HDL, and LDL)	Month 24 and Month 36
	Creatine kinase	Every 6 months
	Creatinine	All visits
	Gamma-glutamyl transferase (GGT)	All visits
	Glucose	All visits
	Glycosolated hemoglobin (HbA1c)	Annually
	Lactic dehydrogenase (LDH)	All visits
	Magnesium	All visits
	Phosphorous, inorganic	All visits
	Potassium	All visits
	Protein, total	All visits
Sodium	All visits	
Triglycerides	Annually	
C-reactive Protein	All visits	

Test Type	Test Parameters	Collection at Visits
Urinalysis	Complete urinalysis (to include urine protein, creatinine, blood, urine microscopy).	All visits

QMD Ref: [REDACTED]	Effective: 12Aug2019	Governing QMD: [REDACTED]
Confidentiality Statement		
This document is the property of [REDACTED] and may not be duplicated, copied, altered or removed from company without prior approval from [REDACTED] or in compliance with [REDACTED].		

REF: [REDACTED]

		Controlled Quality Management Document	
		Sponsor:	Aurinia Pharmaceuticals
		Protocol Number:	AUR-VCS-2016-02
STATISTICAL ANALYSIS PLAN. PHASE 2-3-4			

Test Type	Test Parameters	Collection at Visits
Proteinuria	FMV will be performed to analyze UPCR. A 24-hour urine may be substituted for FMV if required.	All visits
	FMV	All visits
	24-hour urine	Every 6 months

Test Type	Test Parameters	Collection at Visits
Pregnancy Test	A serum pregnancy test will be performed for females of childbearing potential. Urine pregnancy tests will be done using a dipstick.	Month 12, Month 24, and Month 36 (Serum)
		Month 12, Month 15, Month 18, Month 21, Month 27, Month 30, Month 33 (Urine)

Test Type	Test Parameters	Collection at Visits
Lupus Markers	Anti-double-stranded DNA (anti-dsDNA) antibodies	All visits
	Serum	All visits
	Complement 3 Complement 4	
Special Tests	Estimated glomerular filtration rate (eGFR)	All visits

Additional eGFR tables will summarize changes from last on treatment value to last off treatment value. The slope of eGFR over time will also be summarized. eGFR slope will be assessed from AURORA 1 baseline to Week 4 and then from Week 4 through to the end of AURORA 2.

A listing of all laboratory measurements recorded throughout the study will be presented.

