### **1.2.5 Potential Toxicities**

Voclosporin has been studied in numerous disease states. When examining LN, there were a small proportion of voclosporin treated subjects that experienced an early drop of  $\geq 30\%$  in eGFR, however that proportion then remains stable over time. None of these treatment-emergent adverse events (TEAEs) were classed as serious. The majority of TEAEs of decreased GFR were classed as mild or moderate, and resulted in permanent discontinuation of study drug in 1 (1.1%) placebo subject, 7 (7.9%) voclosporin low-dose subjects and

5 (5.7%) voclosporin high-dose subjects. There were more TEAEs of hypertension seen in the voclosporin-treated patients compared to placebo however, overall mean systolic and diastolic BP decreased in all groups, without statistically significant differences seen between groups. Overall, only 1 (1.1%) subject, in the voclosporin high-dose group, had a TEAE of hypertension that resulted in permanent discontinuation of study drug.

There was evidence of an increased incidence of TEAEs over placebo and with increased dose of voclosporin in the System Organ Classes of Infections and Infestations, Gastrointestinal (GI) Disorders, and Vascular Disorders.

There were more deaths in the voclosporin low-dose arm (10) than in either the voclosporin high-dose (2) or placebo (1) arms, with the majority (11/13) occurring in South-East Asia. All deaths were assessed by the Investigator and Data and Safety Monitoring Board (DSMB) as unrelated to study treatment. A full description of AEs can be found in the IB.

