### 2.1 Dose Rationale

The AURORA 2 study is designed to evaluate the safety and tolerability of Orelvo 23.7 mg BID versus placebo, for an additional 24 months following a treatment period of 52 weeks in the AURORA 1 study. Orelvo and/or placebo are herein referred to as study treatment. Subjects will continue to receive the same treatment as assigned by randomization in the AURORA 1 52-week study (either Orelvo or matching placebo). Subjects will continue to receive treatment with study drug at the same dose administered at Week 52 of the AURORA 1 study (see Section 7, [Study Treatments](#)).

Orelvo 23.7 mg BID will continue to be administered as a fixed dose without the use of therapeutic drug monitoring. After 12 months treatment in the AURORA 2 Continuation Study (i.e., 24 months treatment in total), subjects with controlled UPCR (in the Investigator's opinion), taking the 23.7 mg (3 capsules) BID dose will be permitted to reduce the dose of

Orelvo to 15.8 mg (2 capsules) BID if considered appropriate and at the discretion of the Investigator and after consultation with the Medical Monitor.

Population PK analyses of voclosporin concentrations from the clinical development program (including healthy subjects, subjects with renal impairment, subjects with hepatic impairment, renal transplant, and plaque psoriasis) demonstrated that weight did not have a significant effect on the PKs of voclosporin. The protocol contains provisions for management of dose based on safety concerns, in particular, BP and renal function. The safety data from the use of voclosporin demonstrates that these risks are dose-related, reversible, and can be managed by dose reduction and temporary interruption.

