#### **7.6.1.1 Decrease in eGFR $>30\%$ and eGFR $<60$ mL/min/1.73 m^2**

During the treatment period, any subject experiencing a  $>30\%$  decrease in eGFR from AURORA 1 baseline to  $<60$  mL/min/1.73 m^2, will have study treatment interrupted until a repeat test can be performed (unscheduled visit to be completed). If the decrease is confirmed and not due to potential contributing factors (e.g., high baseline eGFR, the addition or modification of non-steroidal anti-inflammatory drugs (NSAIDs), angiotensin converting enzyme (ACE) inhibitors, angiotensin II receptor blockers (ARBs), a concurrent state of dehydration, overdosing with study treatment, lupus renal flare, etc.), the case should be discussed with the Medical Monitor, the study treatment should be withheld, and eGFR retested within 48 hours. If the eGFR decrease is not confirmed, the study treatment can be restarted at 2 capsules BID and increased as tolerated with discussion with the Medical Monitor.

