### **7.6.1.4 Decrease in eGFR $>$ 30% and eGFR $\leq$ 90 mL/min/1.73 m^2**

During the treatment period, any subject having a  $>$ 30% reduction in eGFR from AURORA 1 baseline to  $\leq$ 90 mL/min/1.73 m^2, should have the influence of potential contributing factors (as described in Section 7.6.1.1, [Decrease in eGFR  \$>\$ 30% and eGFR  \$<\$ 60 mL/min/1.73 m^2](#)) ruled out and a confirmation measurement done within approximately 2 weeks (at a planned study visit, if any, or an unscheduled visit is to be completed). The subjects will be managed in the most medically appropriate manner in consultation with the Medical Monitor.

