### **9.2.5 Unscheduled Visit**

Unscheduled visits may be performed during the course of the study for safety reasons. An unscheduled visit is required 2 weeks after dose reduction at any time during the study. Only the data relevant to the purpose of the visit will be collected in the source documents and eCRF. An unscheduled visit is requested in the following cases:

- QTcF value exceeding 500 msec, or an increase  $>60$  msec from baseline, where the ECG will be repeated (confirmed) at an unscheduled visit
- Systolic BP is  $\geq 165$  mmHg or diastolic BP is  $\geq 105$  mmHg, or confirmed systolic BP  $>130$  mmHg or a diastolic BP  $>80$  mmHg
- Decrease in eGFR  $>30\%$  compared to baseline, or a confirmed decrease in eGFR  $>20-30\%$  compared to baseline (detailed in Section [7.6.1, Deterioration in Renal Function](#))

Additional unscheduled visits may be planned per Investigator's judgment.

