3.1 Primary Endpoint

Adverse event (AE) profile and routine biochemical and hematological assessments. Estimand for AEs is the proportion of subjects reporting AEs in the Safety Population when comparing voclosporin and placebo at each visit. Estimands for biochemical and hematological assessments are the mean absolute values and mean changes from AURORA 1 baseline in the Safety Population when comparing voclosporin and placebo at each visit.

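### The visible SAP has no by-arm count of large eGFR falls, and its laboratory tabulation rules can leave such falls out of the visit tables; one descriptive table would close the gap cheaply

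*SAP*

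**What the plan says.** **The renal signal.** Protocol 1.2.5 says that a small share of voclosporin-treated lupus nephritis subjects had an early eGFR loss of at least 30%, "however that proportion then remains stable over time". The same section gives permanent discontinuations for decreased GFR: 1 (1.1%) on placebo, 7 (7.9%) on low dose and 5 (5.7%) on high dose. Low dose was 23.7 mg BID, the dose studied here. Of the blood pressure and renal risks, Protocol 2.1 says that "these risks are dose-related, reversible, and can be managed by dose reduction and temporary interruption".

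**Protocol actions on a fall from AURORA 1 baseline.**
- More than 30%, to below 60 (7.6.1.1): drug is interrupted pending a repeat test. "If the eGFR decrease is not confirmed, the study treatment can be restarted at 2 capsules BID".
- More than 30%, to 90 or below (7.6.1.4): contributing factors are to be "ruled out and a confirmation measurement done within approximately 2 weeks".
- More than 20% and up to 30%, to below 60 (7.6.1.2): re-measurement in about 2 weeks.
- More than 30%, staying above 90 (7.6.1.5): monitoring only.
- Any decrease above 30% (9.2.5): an unscheduled visit is requested. Also, "An unscheduled visit is required 2 weeks after dose reduction at any time during the study".

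**SAP outputs.** SAP 3.1 sets the laboratory estimand: "Estimands for biochemical and hematological assessments are the mean absolute values and mean changes from AURORA 1 baseline in the Safety Population". SAP 6.11.2.4 and 6.12.2 add MMRM, change from last on-treatment to last off-treatment value, and listings. "The slope of eGFR over time will also be summarized", split at Week 4.

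**SAP tabulation rules.** SAP 6.2.12 maps every visit to the nearest scheduled one and tabulates the latest value. The closing paragraph of SAP 6.2.18, placed under the SF-36 heading, tabulates scheduled laboratory values only. SAP 6.2.14 caps eGFR at 90 in eGFR tables and endpoints, with raw values kept for change-from-baseline tables and listings.

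**The concern.** The protocol treats a fall of more than 30% as the point at which something must be done for the individual subject. The SAP reports eGFR mainly through averages, and an average can hide a fall confined to a minority. The values that protocol action generates are unscheduled and repeat measurements, and these are the ones the tabulation rules discard or allow to overwrite the first low value. A reader of the by-arm eGFR tables would therefore be unable to say how many subjects in each arm had a large fall up to Month 36, or whether the proportion mentioned in Protocol 1.2.5 stayed stable over the longer period.

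**Working it through.** The plan states no figure to reproduce here. The check has four steps.

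**1. Could a planned output stand in for the count?**
- *eGFR component of renal response (SAP 6.11.1, 6.11.2.1).* It passes any value of 60 or more, so 100 to 62 (62/100 - 1 = -38%) passes. It also excuses a confirmed fall above 20% to below 60 when no related eGFR adverse event is present. This is the only percent-fall limit in the visible SAP.
- *Normal-range shifts (6.12.2).* They classify values against a laboratory range, not against the subject's own baseline.
- *TEAE tables (6.12.1).* They will catch many cases, because Protocol 10.2.4 and 10.2.5 make worsening and normal-to-pathological shifts recordable. They still rest partly on investigator judgement of clinical relevance and of normal disease fluctuation.
- *Dose-change summaries (6.9).* They are not described by reason, so they would mix eGFR-driven changes with the optional reduction after Month 24 and with GI or blood-pressure changes.

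**2. The tabulation rules, for an illustrative subject with baseline 85.** Percent change = value/85 - 1.

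| Sequence | Latest value per visit (6.2.12) | Scheduled only (6.2.18) |
|---|---|---|
| Month 18 = 55 (-35.3%); drug interrupted; retest 72 (-15.3%) | 72 shown; fall lost | 55 shown |
| Month 18 = 80 (-5.9%); unscheduled 55 at Month 20 (-35.3%); Month 21 = 78 (-8.2%) | 78 shown at Month 21; fall lost | 80 and 78 shown; fall lost |
| As row 2, but the 55 falls at Month 19 | 55 shown at Month 18 | fall lost |

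The rules disagree in rows 1 and 3, and both lose the fall in row 2.

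**3. The cap.** Corrected eGFR = min(eGFR, 90).
- A raw fall above 30% ending at 63 or more needs a baseline above 63/0.7 = 90. Its corrected fall is at most 1 - 63/90 = 30%, so it drops below the limit. Example: 120 to 80 is -33.3% raw and 80/90 - 1 = -11.1% corrected.
- A raw fall above 30% ending at e below 63 stays above 30%: from a baseline above 90 the corrected fall is 1 - e/90 > 30%; from 90 or below nothing changes. Example: 120 to 59 is -50.8% raw and 59/90 - 1 = -34.4% corrected.
- A fall ending below 60 from a baseline above 90 has a corrected fall above 1 - 60/90 = 33.3%. Raw and corrected counts therefore agree for any limit of 20% or 30% that also requires a value below 60.

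A grid check (baseline 30 to 160, step 0.5) agreed: 6,972 of 6,972 falls above 30% ending at 63 or more were reduced to 30% or less, 0 of 22,638 ending below 63 were, and 0 of 22,860 falls above 20% ending below 60 dropped to 20% or less.

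**4. Means versus a count.** All inputs in this step are assumptions except the total of 216 (SAP 6.1.2): 108 per arm, and 10% more voclosporin subjects losing an extra 30 mL/min.
- Shift in the mean = 0.10 x 30 = 3 mL/min.
- SE = SD x sqrt(2/108) = 2.04, 2.72 and 3.40 for SD 15, 20 and 25.
- Two-sided 5% power, approximately Phi(3/SE - 1.96), is 31%, 20% and 14%.
- For the count, SE = sqrt[p0(1 - p0)/108 + p1(1 - p1)/108]. The risk difference with 95% CI is 10 points (0.6 to 19.4) for 10% versus 20%, 10 points (2.1 to 17.9) for 5% versus 15%, and 5 points (-2.0 to 12.0) for 5% versus 10%.

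The count is not highly precise, but it displays the subjects that the mean dilutes.

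**The case against.** The strongest reply is that no commitment is broken. Protocol 1.2.5 is background from earlier studies. It gives no figure for the 30% proportion, and the figures it does give are discontinuations for decreased-GFR TEAEs. The SAP plans that metric by preferred term, by dose modification and discontinuation, by year of onset, and as exposure-adjusted rates. Protocol 13.9 promises absolute values, changes and out-of-range summaries, and SAP 6.12.2 supplies them. All of this stands, and it is why the point is an improvement and not an error.

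The two tabulation rules also conflict, and the scheduled-only rule is the one specific to laboratory data. If it governs, row 1 of the table is not masked. That is correct, but rows 2 and 3 are then lost. An interruption in row 2 would show in the dose summaries, though not as an eGFR fall.

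Four stronger readings are tempting and are not supported:
- *That no such table exists anywhere.* SAP text from 6.11.8 to the start of 6.12.1, and some text between 6.12.2 and 6.12.3, is not available, and the DSMB outputs have a separate SAP (SAP 8).
- *That every fall above 30% triggers interruption or retest.* A fall that stays above 90 is only monitored under Protocol 7.6.1.5, although 9.2.5 still requests a visit.
- *That the cap hides serious falls.* It affects only falls ending at 63 or above, and raw change tables are planned.
- *That renal safety data are lost.* Every value is listed, and SAP 6 allows further tables in the study report.

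There is also a fair caution about any count: Protocol 7.6.1 warns that eGFR is unreliable above 100 and can fluctuate widely. Any-fall counts depend on how often eGFR is measured, and the extra visit after a dose reduction may make that differ by arm.

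**Conclusion.** The point holds as a low-cost improvement. The visible SAP has no by-arm count at the limit on which the protocol acts, and its laboratory rules can leave such falls out of the by-arm eGFR visit tables. TEAE tables will catch many of these falls but not necessarily all.

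Its size cannot be stated in subjects, because the documents give neither the rate of falls above 30% in AURORA 2 nor the split of the 216 subjects by arm. The power and interval figures illustrate the mechanism under assumed values only. What is missing is a prespecified count, with stated handling of unscheduled values, post-interruption retests and the eGFR scale. The conclusion is limited to the SAP text available.

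**What to change.** In SAP 6.12.2, add one descriptive by-arm table of subjects with a post-baseline eGFR fall from AURORA 1 baseline (as defined in SAP 6.2.2) of (a) more than 30%, (b) more than 30% to below 60, and (c) more than 20% to below 60, with risk difference and 95% CI.

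- **Values:** all scheduled, unscheduled and repeat central-laboratory results, as a stated exception to SAP 6.2.12 and the closing rule of 6.2.18.
- **Populations and periods:** the AURORA 2 safety population (n=216) over AURORA 2 and over Months 0-36, and the AURORA 1 safety population (n=356) over Months 0-36. Entry required 52 completed weeks of treatment, so a Month 0-36 count in the 216 alone would omit the 356 - 216 = 140 who did not continue, including any who stopped for eGFR decline.
- **Scale:** raw and corrected. By step 3 the two can differ only in (a), so (b) and (c) need printing once.
- **Ascertainment:** any-fall, confirmed-fall and scheduled-visits-only rows side by side. State what counts as confirmed, since a retest under Protocol 7.6.1.1 follows interruption of drug.

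That makes 4 distinct definitions x 3 ascertainment versions x 3 population-period sets = 36 lines, all from data already collected and with no burden on subjects. The costs are SAP wording and a little programming. Some counts will reflect fluctuation at high eGFR, and ascertainment may differ by arm; the corrected and scheduled-only rows help the reader to judge both.

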6.12.3 Vital Signs

Descriptive statistics for observed values and changes from baseline in the following vital signs will be presented by treatment group and visit:

- Systolic blood pressure (mmHg)
- Diastolic blood pressure (mmHg)
- Pulse rate (bpm)
- Body temperature (degrees Celsius).

Mean values for systolic and diastolic blood pressure will be used in the summary tables. Where the mean value is unavailable, an individual measure at the visit in question will be used.

Listings of all vital sign measurements will be provided.

